## 2.2 Hypotheses and/or Estimations

The primary clinical hypothesis is that preventive treatment with monthly injections of erenumab is superior to placebo in reducing disability in employed subjects with EM who have previously failed 1 or more migraine preventive treatments.

### **3. Study Overview**

#### **3.1 Study Design**

Study 20180060 is a phase 4, 24-week, prospective, double-blind, randomized, placebo-controlled, multicenter study in the United States (US), evaluating the effect of erenumab on disability and work productivity in employed patients with EM who have previously failed 1 or more migraine preventive treatments. Subjects will enter initial screening (up to 21 days) to determine if they meet Eligibility Criteria Part 1. If Part 1 eligibility criteria are met, subjects will enter baseline (28 days). After subjects complete baseline and are found eligible based on Eligibility Criteria Part 2, they will be enrolled and randomized in a 1:1 ratio to either erenumab 140 mg or placebo. Randomization will be performed separately within traditional sites and decentralized clinical trial site (DCTS). Subjects will then enter a 24-week DBTP which will conclude with an end-of-study visit at week 24.

#### **3.2 Sample Size**

The total sample size of 240 subjects (120 subjects per treatment group) enrolled from traditional sites will provide at least a 94% power for the primary efficacy hypothesis. The statistical power for secondary efficacy hypotheses ranges from 88% to 99%. This sample size is not inflated for dropouts since subjects who drop out early during the 6-month DBTP are likely to have at least 1 post-baseline measurement and therefore will still be included in the analysis based on the primary estimand utilizing a repeated measures linear mixed model approach. [Table 3-1](#) provides sample size assumptions and resulting statistical power for each hypothesis.

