#### **9.1.2 Treatment Period**

Study visits will occur per the Schedule of Activities ([Table 2-1](#)). The date of the first dose of IP is defined as day 1 and must occur 28 to 35 days from the Day -28 visit. On-study visits after Day 1 may be completed within  $\pm 3$  days. All subsequent doses and study visits will be scheduled based on the day 1 date. Administration of protocol-required therapies is to be administered once every 4 weeks during each visit that it is required.

Subjects who discontinue IP are encouraged to remain in the study and complete all remaining procedures and study visits.

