## **10. Statistical Considerations**

### **10.1 Sample Size Determination**

The total sample size of 240 subjects (120 subjects per treatment group) enrolled from traditional sites will provide at least a 94% power for the primary efficacy hypothesis.

The statistical power for secondary efficacy hypotheses ranges from 88% to 99%. This sample size is not inflated for dropouts since subjects who drop out early during the 6-month DBTP are likely to have at least 1 post-baseline measurement and therefore will still be included in the analysis based on the primary estimand utilizing a repeated measures linear mixed model approach. [Table 10-1](#) provides sample size assumptions and resulting statistical power for each hypothesis.

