**Table 10-1. Sample Size Assumptions and Statistical Power for Traditional Sites**

Hypothesis	Assumed Treatment Effect (Erenumab – Placebo)	Assumed Common Standard Deviation	Power for Sample Size of 240 Subjects
Primary: modified MIDAS total score	-20	43	94%
Secondary:			
• MMD	-2.0	3.4	> 99%
• Work productivity impairment (WPAI)	-10.0	23.1	91%
• MFIQ physical function	-7.6	16.2	95%
• MFIQ usual activities	-6.1	14.9	88%
• MFIQ social function	-6.8	15.6	91%

MFIQ = Migraine Functional Impact Questionnaire; MIDAS = Migraine Disability Assessment; MMD = monthly migraine days; WPAI = Work Productivity and Activity Impairment.

Note: All power calculations are based on a 2-sided significance level of 0.05 and not adjusted to reflect the sequential testing procedure. The assumed treatment effects and common standard deviations for modified MIDAS, MMD, and MFIQ hypotheses are derived from a subset of subjects in erenumab Study 20120296 satisfying the key entry criteria of the current study. The assumed treatment effect and common standard deviation for the work impairment hypothesis is derived from the LIBERTY study.

In addition, a total sample size of 100 subjects (50 per treatment group) will be enrolled as part of the DCTS for pilot purposes.

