### **10.4.2 Methods of Analyses**

#### **10.4.2.1 General Considerations**

All analyses will be conducted separately for subjects enrolled from traditional sites and subjects from DCTS. Formal statistical hypothesis testing for the primary and secondary endpoints will be performed for subjects enrolled from traditional sites only. Subject characteristics for both traditional sites and DCTS will be summarized descriptively.

Summary statistics by each treatment group will be tabulated at each assessment time point if applicable. For continuous endpoints, the descriptive statistics include: number of observations, means, medians, standard deviations, standard errors, first and third quartiles, minimums and maximums, and 2-sided 95% CIs of the means (CIs will be provided for efficacy endpoints only). For categorical endpoints, the summaries will contain the number and percentage of subjects in each category.

The primary analysis method utilizing a repeated measures linear mixed effects model will include all observed data regardless of treatment adherence.

A sequential testing procedure will be used to maintain the family-wise type 1 error  $\alpha = 0.05$  between the primary and secondary endpoints following the order of modified MIDAS, MMD, WPAI, MFIQ physical function, MFIQ usual activity, and MFIQ social function endpoints. An endpoint will only be tested if the endpoint tested in the previous step is statistically significant at 2-sided significance level of 0.05.

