#### **4. Covariates and Subgroups**

##### **4.1 Planned Covariates**

All model-adjusted analyses of efficacy endpoints will include the corresponding baseline value for the endpoint being analyzed.

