### 9.5.1 Analyses of Primary and Secondary Efficacy Endpoints

The primary analysis of the primary and secondary endpoints will be performed using a generalized linear mixed model based on observed monthly data with appropriate contrasts for treatment comparison relative to placebo for the corresponding efficacy endpoints: sum of monthly changes from baseline value over the 6-month DBTP, and change from baseline in mean monthly values or mean domain scores over months 4, 5 and 6. The model will include treatment, scheduled visit, treatment-by-visit interaction, and baseline value as covariates. If applicable, the first-order autoregressive covariance structure is assumed. Least squares means (LSMs) for each treatment group, standard errors, associated 95% confidence intervals, difference of LSMs compared to placebo group, associated 95% confidence intervals and nominal two-sided p-values will be tabulated by visit, as well as for the mean monthly values over months 4, 5, and 6 of the DBTP.

Sensitivity analysis described below will be performed for the primary and secondary endpoints:

1. MI with assumption of MNAR (control-based pattern imputation).
2. Primary summary and analysis by the subgroup of treatment failure of prior migraine prophylactic medications (Section 4.2)

The purpose of the subgroup analyses is to explore if the treatment effect varies across subgroups of interest. Analysis within each interested subgroup will be performed using the same primary analysis method for the same endpoint. The treatment difference with associated 95% confidence interval and p-value will be reported within each subgroup.

The heterogeneity of the treatment effect across the subgroups will be evaluated by examining the treatment-by-subgroup interaction p-value obtained from the primary analysis model with the addition of treatment-by-subgroup interaction.

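### Do the stated secondary powers of 88% to 99% need restating because of the fixed test sequence and dropout?

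*SAP*

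**What the plan says.** SAP 3.2 bases its power on "The total sample size of 240 subjects (120 subjects per treatment group) enrolled from traditional sites" and gives at least 94% for the primary hypothesis. It continues: "The statistical power for secondary efficacy hypotheses ranges from 88% to 99" percent. Table 3-1 (Table 10-1 in the protocol) gives the effect, SD and power for each endpoint. Its note states that the calculations are two-sided at 0.05 and "not adjusted to reflect the sequential testing procedure".

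The sequence is set out in Protocol 10.4.2.1 and SAP 9.1: "An endpoint will only be tested if the endpoint tested in the previous step is statistically significant at 2-sided significance level of 0.05". The order is modified MIDAS, MMD, WPAI, MFIQ physical function, MFIQ usual activities, MFIQ social function.

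On dropout, the sentence in Protocol 10.1 that begins "This sample size is not inflated for dropouts since subjects who drop out early" goes on to argue that such subjects will probably have a post-baseline value and so stay in the mixed-model analysis. No dropout rate is given.

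Two other provisions bear on the point. SAP 4.1 states: "All model-adjusted analyses of efficacy endpoints will include the corresponding baseline value for the endpoint being analyzed". Protocol 9.1.2 states: "Subjects who discontinue IP are encouraged to remain in the study and complete all remaining procedures and study visits".

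**The concern.** There are two strands.

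First, no secondary endpoint is ever tested alone. To reject at a given step, the trial must also reject at every earlier step, so the chance of a formal result cannot exceed the lowest single-test power up to that point. A reader who takes the text sentence by itself would credit MMD with more than 99% and MFIQ social function with 91%. Neither is attainable under the sequence.

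Second, membership of the analysis set is not the same as full information. All five secondary endpoints average months 4, 5 and 6. A subject seen only in months 1 to 3 has no value in that window and informs the contrast only through within-subject correlation. The argument that dropouts remain in the model therefore does not by itself show that power is kept.

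If both strands mattered, the stated chance of success for the five secondary claims would be too high, and the case for 240 subjects weaker than it looks.

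**Working it through.** **Inputs.** Effects and SDs are from Table 3-1; n = 120 per arm; two-sided 0.05; test order from SAP 9.1. Correlations between endpoints, dropout rates and within-subject correlations are not in the documents and are assumed, with ranges.

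**Step 1: reproduce the stated powers.** Noncentrality = effect / (SD × √(2/120)), with √(2/120) = 0.1291. The normal approximation to power is Φ(noncentrality − 1.96). The t column uses the noncentral t distribution.

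| Endpoint | Effect / SD | Noncentrality | Normal | t-test | Stated |
|---|---|---|---|---|---|
| Modified MIDAS | 20 / 43 | 3.60 | 95.0% | 94.8% | 94% |
| MMD | 2.0 / 3.4 | 4.56 | 99.5% | 99.5% | >99% |
| WPAI | 10.0 / 23.1 | 3.35 | 91.8% | 91.6% | 91% |
| MFIQ physical | 7.6 / 16.2 | 3.63 | 95.3% | 95.2% | 95% |
| MFIQ usual activities | 6.1 / 14.9 | 3.17 | 88.7% | 88.5% | 88% |
| MFIQ social | 6.8 / 15.6 | 3.38 | 92.2% | 92.0% | 91% |

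The t-test values match the table when truncated to whole percent (92.0% for social is 91.97% before rounding). The plan's figures are correct single-test powers.

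**Step 2: ceilings under the sequence.** The ceiling at each step is the running minimum of the powers up to that step, and needs no correlation assumption. From the plan's own figures:

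- MMD: min(94, >99) = 94%, stated >99%
- WPAI: min(94, 91) = 91%, stated 91%
- MFIQ physical: min(91, 95) = 91%, stated 95%
- MFIQ usual activities: min(91, 88) = 88%, stated 88%
- MFIQ social: min(88, 91) = 88%, stated 91%

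Three of the five are capped below the stated value, by about 5, 4 and 3 points. The primary is tested first and loses nothing.

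**Step 3: below the ceilings.** Going further needs a correlation between endpoints. With an assumed common correlation from 0 to 0.9 and the t-test powers, the chance of rejection is:

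- MMD 94.4-94.8%
- WPAI 86.4-90.6%
- MFIQ physical 82.2-90.0%
- MFIQ usual activities 72.8-86.1%
- MFIQ social 66.9-85.2% (76.0% at 0.5, 80.2% at 0.7)

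The lowest values come from zero correlation, which is implausible for six measures of migraine burden, three of them domains of one questionnaire.

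**Step 4: dropout, single-test power.** Assume 10-20% total loss spread evenly after months 1 to 5, with every dropout having at least one post-baseline value. SAP 9.5.1 says of the covariance: "If applicable, the first-order autoregressive covariance structure is assumed". Taking AR(1) at 0.5-0.8 or compound symmetry at 0.5-0.7, the information matrix of the six-visit model gives:

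- Six-month sum (primary): effective n of 110.8-118.8 per arm, power 93.1-94.6% against 94%.
- Months 4-6: effective n of 103.5-117.3 per arm. Usual activities has 83.4-87.7% against 88%, and social has 87.7-91.4% against 91%.

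**Step 5: possible offset from baseline adjustment.** If the planning SDs are not baseline-adjusted, a baseline-outcome correlation r multiplies the variance by 1 − r². The r that restores n = 120 is √(1 − n_eff/120):

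- n_eff = 103.5: √(1 − 0.8625) = 0.37
- n_eff = 117.3: √(1 − 0.9775) = 0.15

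A baseline correlation of 0.15 to 0.37 would therefore cancel the loss in full.

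**The case for a change.** The best case for a change is that the ceilings follow from the sponsor's own table without any outside assumption, that the sentence in the text carries no qualifier, and that the table note gives neither the direction nor the size of the effect. Calling the figures single-test power where they are stated, and adding one column, would cost almost nothing.

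Much of this stands as description. The sentence does not repeat the caveat, no sequence-adjusted figure is shown, and the reason given for no dropout allowance is incomplete for endpoints confined to months 4-6. However, the text sends the reader directly to the table, and the note sits under it in the same section, so the limitation is disclosed where the figures are. A sequence-adjusted power beyond the ceilings would need correlations that the documents do not supply.

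The dropout strand is weaker. The sentence justifies N by reference to the primary estimand, and the primary keeps 93.1-94.6%. The SDs come from earlier studies, and the documents do not say whether they come from completers or are already baseline-adjusted. Part of the loss may already be counted, and the net effect on power cannot be determined from the plan. Subjects who stop treatment are encouraged to stay, and those who leave the study complete the end-of-study assessments (Protocol 9.1.3), which supports the expectation of at least one post-baseline value.

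**Conclusion.** No change follows. The secondary powers are right as single-test figures, and the plan says that they ignore the sequence. A statistician reading Table 3-1 with its note can obtain the ceilings of 94, 91, 91, 88 and 88% by taking running minima.

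The part that is certain is a reduction of about 3 to 5 points for three secondary endpoints (MMD, MFIQ physical, MFIQ social). Anything larger rests on an assumed correlation. The dropout effect is modest: under an assumed 10-20% loss it leaves the primary within about a point of 94% and takes usual activities to 83.4-87.7%. Baseline adjustment could offset the months 4-6 loss if the planning SDs are unadjusted.

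On either reading, N stays at 240, the test order and model stay as written, type I error is controlled, and no estimate or decision rule depends on the power sentence. Repeating the caveat in the text would be a matter of presentation and would not alter how the trial is run, analysed or interpreted.

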**Table 3-1. Sample Size Assumptions and Statistical Power for Traditional Sites**

Hypothesis	Assumed Treatment Effect (Erenumab – Placebo)	Assumed Common Standard Deviation	Power for Sample Size of 240 Subjects
Primary: modified MIDAS total score	-20	43	94%
Secondary:			
• MMD	-2.0	3.4	> 99%
• Work impairment (WPAI)	-10.0	23.1	91%
• MFIQ physical function	-7.6	16.2	95%
• MFIQ usual activities	-6.1	14.9	88%
• MFIQ social function	-6.8	15.6	91%

MFIQ = Migraine Functional Impact Questionnaire; MIDAS = Migraine Disability Assessment; MMD = monthly migraine days; WPAI = Work Productivity and Activity Impairment.

Note: All power calculations are based on a 2-sided significance level of 0.05 and not adjusted to reflect the sequential testing procedure. The assumed treatment effects and common standard deviations for modified MIDAS, MMD, and MFIQ hypotheses are derived from a subset of subjects in erenumab Study 20120296 satisfying the key entry criteria of the current study. The assumed treatment effect and common standard deviation for the work impairment hypothesis is derived from the LIBERTY study.

In addition, a total sample size of 100 subjects (50 per treatment group) will be enrolled as part of the DCTS for pilot purposes.

#### **4. Covariates and Subgroups**

##### **4.1 Planned Covariates**

All model-adjusted analyses of efficacy endpoints will include the corresponding baseline value for the endpoint being analyzed.

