### Rationale:

The presence of various comorbidities in migraine patients, whether associated or migraine-induced, has been established by numerous studies. These comorbidities contribute to migraine-related disability, impacting work and overall function (Lipton et al, 2013; Stewart et al, 2008). The American Migraine Prevalence and Prevention (AMPP) study of patients with episodic migraine (EM) evaluated several domains of headache-related disability such as work, depression, and anxiety, to name a few, that are frequently affected by migraine. Other studies, though smaller in scale, have demonstrated the impact of migraine on quality and quantity of sleep (Barbanti et al, 2007; Kelman and Rains, 2005).

Closer analyses of impact of migraine on work have not only revealed absence from work, but also reduction in performance also known as presenteeism (Stewart et al, 2008). Relevant components of decreased presenteeism include impaired concentration and feeling of fatigue.

In phase 2 and 3 clinical trials, erenumab-aooe (referred to as erenumab herein) has demonstrated a reduction in monthly migraine days (MMD) as well as migraine-related disability (Dodick et al, 2018; Tepper et al, 2017; Goadsby et al, 2017b). **Separately,** improvement in MMD and migraine-related disability have been associated with improvement in work productivity (Dodick et al, 2016; Lipton et al, 2013).

Study 20180060 is being conducted to confirm the effect of erenumab on migraine-related disability (inclusive of aforementioned comorbidities) and work productivity.

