### Other Exclusions

- 217 Female subject is pregnant or breastfeeding or planning to become pregnant or breastfeed during treatment and for an additional 16 weeks after the last dose of IP
- 218 Female subject of childbearing potential is unwilling to use an acceptable method of effective contraception during treatment and for an additional 16 weeks after the last dose of IP. Refer to [Section 12.5](#) for additional contraceptive information.
- 219 Female subject of childbearing potential has a positive pregnancy test assessed at screening by a urine pregnancy test
- 220 Likely to be unavailable or unable to complete all protocol-required study visits or procedures, and/or to comply with all required study procedures to the best of the subject and investigator's knowledge
- 221 History or evidence of any other clinically significant disorder, condition or disease (with the exception of those outlined above) that, in the opinion of the investigator or Amgen physician, if consulted, would pose a risk to subject safety or interfere with the study evaluation, procedures or completion
- 222 Related to investigational study site staff or investigator

### 6.3 Inclusion Criteria Part 2

Subjects will be assessed at the end of the baseline period and prior to enrollment into DBTP.

Based on information collected through the electronic diary (eDiary) during baseline, the following requirements must be met:

- 109 Has EM defined as  $\geq 4$  and  $< 15$  migraine days and  $< 15$  headache days during baseline (see [Section 12.1](#) for definition of headache/migraine days)
- 110 Employed  $\geq 20$  hours/week upon entry into baseline and has not specified willful termination of employment throughout the duration of the study. Employment is defined by work outside the home, self-employed, or works from home.
- 111 Has  $\geq 4$  hours of lost productive time **due to headache/migraine and/or related symptoms** in the past month during baseline as assessed on Day 1 **by eDiary device** (prior to randomization)
- 112 Has total disability score of  $> 3$  as assessed by modified MIDAS (1-month recall) during baseline as assessed on Day 1 (prior to randomization)

- 114 Demonstrated at least 75% compliance with the eDiary and had at least 3 WPAI measurements during baseline

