## 7.2 Method of Treatment Assignment

Subjects will be enrolled and randomized in a 1:1 ratio to either erenumab or placebo.

Randomization will be performed separately within traditional sites and DCTS.

The randomization will be performed by IRT, and the randomization number will be assigned by IRT and appear on the IRT randomization document. The randomization number is different than the subject identification number and will not be utilized by the site as a subject identifier.

The randomization date is to be documented in the subject's medical record/source documentation and on the enrollment CRF.

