### **Migraine Functional Impact Questionnaire (MFIQ)**

The MFIQ version 2.0 is a self-administered 26-item instrument measuring the impact of migraine on broader functioning including 4 domains: Impact on Physical Functioning (5 items), Impact on Usual Activities (10 items), Impact on Social Functioning (5 items), and Impact on Emotional Functioning (5 items). In addition, there is 1 stand-alone global item assessing the overall impact on usual activities. Subjects respond to items using a 5-point scale assigned scores from 1 to 5, with 5 representing the greatest burden. Each domain score will be calculated as the sum of the item responses and the sum will be rescaled to a 0 to 100 scale, with higher scores representing greater burden. The recall period is the past 7 days and will be collected monthly during baseline and post-baseline.

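### The three MFIQ models adjust only for a one-week MFIQ baseline; adding baseline MMD, which is already collected, would be a small, nearly free gain in precision

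*SAP*

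**What the plan says.** **Covariates.** SAP 4.1 states: "All model-adjusted analyses of efficacy endpoints will include the corresponding baseline value for the endpoint being analyzed". Protocol 10.2.2 says the same. SAP 9.5.1 and Tables 9-1 and 9-2 give the primary and secondary models as treatment, scheduled visit, their interaction and the baseline value. The sensitivity ANCOVA in Protocol 10.4.2.2 has treatment and baseline value only.

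**MFIQ baseline.** SAP 5.1.3 says of the MFIQ: "The recall period is the past 7 days and will be collected monthly during baseline and post-baseline". SAP 5.3 and Table 5-3 take the last measurement on or before Day 1. The Schedule of Activities (Protocol Table 2-1) has no MFIQ before Day 1. The endpoint averages months 4, 5 and 6.

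**Baseline diary.** The eDiary is completed every day through a 28-day baseline with a window of +7 days (Protocol 1, Procedures; Table 2-1, footnote b). Criterion 109 in Protocol 6.3 requires a baseline migraine-day count, and criterion 114 requires that the subject "Demonstrated at least 75% compliance with the eDiary". SAP 9.4 already lists baseline MMD among the baseline characteristics.

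**Randomisation.** Protocol 7.2: "Randomization will be performed separately within traditional sites and DCTS". No prognostic stratification factor is named.

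**The concern.** One week is a short sample of an episodic disease. A subject with a good or bad week before Day 1 has an MFIQ baseline that misstates usual severity, so adjusting for it removes only part of the between-subject variation in the later scores. Baseline MMD covers at least four times as long and could account for some of the rest. Randomisation is not stratified by severity, so chance imbalance in migraine frequency is also left to the MFIQ baseline to absorb.

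At stake is some precision in the last three of six ordered tests. MFIQ usual activities has the lowest stated power (88%) and comes fifth in the sequence. If it fails, MFIQ social function is not tested.

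**Working it through.** **Inputs.** SAP 3.2: "The total sample size of 240 subjects (120 subjects per treatment group) enrolled from traditional sites", and SAP 3.1: "enrolled and randomized in a 1:1 ratio to either erenumab 140 mg or placebo", so n = 120 per arm. SAP Table 3-1 note: "All power calculations are based on a 2-sided significance level of 0.05 and not adjusted to reflect the sequential testing procedure". Effects and SDs are from Table 3-1.

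**Step 1: reproduce the stated power.** SE = SD × √(2/120). The noncentrality is effect/SE, with 238 df and a two-sided 5% test. For usual activities, SE = 14.9 × √(2/120) = 1.924 and 6.1/1.924 = 3.171, which gives 88.5%.

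| Endpoint | Effect | SD | Stated | Recomputed |
|---|---|---|---|---|
| MFIQ physical function | -7.6 | 16.2 | 95% | 95.1% |
| MFIQ usual activities | -6.1 | 14.9 | 88% | 88.5% |
| MFIQ social function | -6.8 | 15.6 | 91% | 92.0% |

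Unrounded, social function is 91.97%. Cut to whole percents, all three match the table.

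**Step 2: apply an assumed gain.** Let R² be the share of residual variance that baseline MMD explains beyond the MFIQ baseline. The SD becomes SD × √(1 − R²). The equivalent sample size is 240/(1 − R²). For usual activities at R² = 0.05, SD = 14.9 × √0.95 = 14.52, SE = 1.875, noncentrality = 3.253 and power = 90.0%.

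| Assumed R² | Physical function | Usual activities | Social function | CI narrower by | Equivalent N |
|---|---|---|---|---|---|
| 0 | 95.1% | 88.5% | 92.0% | 0 | 240 |
| 0.03 | 95.7% | 89.4% | 92.7% | 1.5% | 247 |
| 0.05 | 96.0% | 90.0% | 93.2% | 2.5% | 253 |
| 0.10 | 96.8% | 91.5% | 94.3% | 5.1% | 267 |

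**Step 3: why 0-10%.** The documents give no correlations, so these are assumptions. Write a for the correlation of MFIQ baseline with outcome (0.4-0.5), b for baseline MMD with outcome (0.2-0.4) and c for baseline MMD with MFIQ baseline (0.3-0.5). The partial correlation is (b − a·c)/√[(1 − a²)(1 − c²)], and R² is its square.

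- a = 0.4, b = 0.2, c = 0.5: numerator 0.2 − 0.2 = 0, so R² = 0.
- a = 0.4, b = 0.3, c = 0.3: 0.18/√(0.84 × 0.91) = 0.206, so R² = 0.042.
- a = 0.4, b = 0.4, c = 0.3: 0.28/0.874 = 0.320, so R² = 0.103.

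**Step 4: cost.** The extra term uses about one degree of freedom. With about 236 residual df, the variance rises by a factor of about 1 + 1/236 = 1.004. An R² above roughly 0.4% therefore pays for itself.

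**Step 5: availability.** Of 28 days, 75% is 21. SAP 5.1.1 needs 14 diary days to derive MMD.

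**The case against.** The strongest reply is that nothing here is wrong. The baseline-adjusted model is prespecified, consistent across both documents and unbiased under randomisation. The benefit is assumed, and Step 3 shows that it can be zero. Criterion 109 limits baseline migraine days to at least 4 and under 15, which tends to weaken any correlation. The Protocol's rationale says that "improvement in MMD and migraine-related disability have been associated with improvement in work productivity". That links changes with changes, and does not show that baseline MMD predicts later MFIQ once the MFIQ baseline is in the model. All of this stands, and is why the point is a modest one.

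The basis of the SDs is also open. Table 3-1 does not say whether they are raw or baseline-adjusted. If they are raw, and the MFIQ baseline explained an assumed 20% of variance, usual-activities power would already be 94.2%, and a further 3-5% reduction would give only 94.8-95.2%.

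A reader might infer more than the documents support in three ways:

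- *That every efficacy model has this weakness.* The noisy-baseline argument fits only the MFIQ. Modified MIDAS recalls a month, WPAI averages weekly scores over baseline with at least 3 required at entry, and the MMD baseline is itself the diary. HRU is summarised without a model.
- *That the primary endpoint gains a known amount.* A variance reduction reasoned from a one-week MFIQ score cannot be carried over to a sum of six monthly changes on a one-month recall scale.
- *That baseline MMD can never be missing.* A diary day needs complete headache, aura and medication data, which is not the same as 75% eDiary compliance. Subjects may be found ineligible after enrolment (Protocol 9). The efficacy set requires only the endpoint's own baseline. Gaps should be rare but need a rule.

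None of this shows a material downside to the change for the MFIQ endpoints.

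**Conclusion.** The point holds as a small efficiency gain for the three MFIQ secondary endpoints. It is not an error, and the stated power figures stand. With an assumed 0-10% reduction in residual variance, usual-activities power is about 88.5-91.5%, with 89.4-90.0% at 3-5%; the latter equals about 7 to 13 extra subjects. These figures rest on correlations that the documents do not give and on reading the Table 3-1 SDs as residual SDs. The true gain may be close to nil.

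The change is still worth making because it uses a value the trial already has, costs about one degree of freedom and leaves the difference-in-means estimand unchanged. The same term could be used for modified MIDAS and WPAI, but their baselines already cover about a month, so less should be expected there.

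**What to change.** Before unblinding:

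1. In SAP 4.1, Table 9-2 and 9.5.1, add baseline MMD as a second covariate in the mixed models for MFIQ physical function, usual activities and social function.
2. Add it to the imputation and analysis models of the MNAR sensitivity analysis for the same three endpoints.
3. State a rule for any missing baseline MMD, for example imputing the covariate with its overall mean, so that no subject leaves the efficacy analysis set because of it.
4. Record the departure from Protocol 10.2.2 and 10.4.2.2 in SAP Section 10.
5. Report the model with the MFIQ baseline alone as supportive.

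The cost is one extra model term and consistent edits in these SAP places. No new data are needed, and the sample size and testing order do not change.
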